Official Title: Comprehensive Wide Bandwidth Test Battery of Auditory Function
in Veterans

NCT Number: 02019888

Document Date: 3/5/2021

Study Protocol

The goal of this research is to evaluate a comprehensive test battery of new wide-bandwidth, i.e., wideband (WB), acoustical tests of auditory function in the differential diagnosis of middle ear, cochlear and neural pathologies in a population of Veterans. WB tests refer to ear canal tests using sound responses measured from 200 Hz to frequencies as high as 8000 Hz, a bandwidth that is critical for speech perception. There will be tests in the battery for middle-ear assessment using absorbance cochlear assessment using otoacoustic emissions (OAEs) and the acoustic stapedius reflex (ASR) using middle ear power absorption. Results will be compared with a standard single-frequency clinical immittance test battery routinely used in the assessment of auditory function in Veterans.

Aim 1 seeks to evaluate the accuracy of the WB test battery in the differential diagnosis of middle-ear pathology and related conductive hearing loss by comparing the sensitivity and specificity of the WB battery to the traditional immittance battery for disorders common in Veterans including tympanic membrane perforation and serous otitis media. Aim 2 seeks to modify a WB ASR test to provide automatic detection of the ASR threshold for comparison with the traditional single-frequency ASR threshold. Aim 3 seeks to validate the use of Transient-evoked otoacoustic emission (TEOAE) and spontaneous otoacoustic emissions (SOAEs) tests in Veterans to assess cochlear status, and evaluate their test performance in classifying ears with normal hearing and sensorineural hearing loss. The combination of tests across aims will allow for examination of the diagnostic accuracy of the full WB test battery in comparison to the single-frequency admittance test battery to detect any type of hearing loss including sensorineural, conductive and mixed. The hypothesis is that the WB test battery is more accurate than the traditional immittance test battery in identifying ears with normal auditory status and ears with a range of risks for auditory pathology.

Methods:

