Subjects- Human subjects will be recruited for this study who have had a hearing evaluation from the VA Audiology Service at the Portland VA Medical Center and the H. Quillen VA Medical Center. These subjects will respond to flyers or be contacted from an IRB-approved human subject volunteer registry. Data will be acquired from three groups of subjects with normal hearing, sensorineural hearing loss (SNHL), and middle ear disorders.

Testing- All subjects will receive the same clinical and WB test battery. Each subject will be tested in one laboratory visit. Subjects will be enrolled in this study that upon otoscopic inspection of their ear canals, have no active drainage from the ears, and have ear canals free of cerumen (wax) impaction, bilaterally. Subjects who are found to have draining ears or cerumen impaction will be referred for treatment. These individuals may be enrolled in the study following successful treatment for their conditions. All subjects will have a standard pure-tone air- and bone-conduction

audiogram while comfortably seated in a sound-treated booth. Standard insert earphones and a bone-conduction vibrator will be used to present the sound stimuli. Next, speech audiometry will be completed and the speech reception thresholds, uncomfortable loudness test for speech, and speech recognition scores will be obtained. Then the subjects will have a standard immittance test battery consisting of a tympanogram and acoustic reflex threshold testing. Stimuli will not exceed a level of 100 decibels hearing level (dB HL). Finally, the wideband test battery will be performed with adults seated comfortably in a sound-treated booth. A small probe with a soft rubber tip will be inserted in the subject's ear canal, and the subject will be asked to remain quiet while sounds are presented to an ear via sound sources within the probe. Responses will be measured using a miniature microphone within the probe. The tests in the wideband battery are similar to the clinical admittance battery and include ambient absorbance, absorbance tympanometry and acoustic reflex threshold. The otoacoustic emission testing is a separate measurement of inner ear function typically conducted in the clinic using different equipment.

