## **Statistical Analysis Plan**

Analyses of variance (ANOVA) will be conducted to examine differences in outcomes measures across the three subject groups with normal hearing (NH), sensorineural hearing loss (SNHL), and middle ear disorders (ME). Bonferroni corrections will be applied for multiple comparisons. T-tests will be used to examine effects of method (clinical vs. experimental wideband) within each subject group.

For the Primary Outcome measure of Middle Ear Test, separate ANOVAs will be used to examine differences across groups within each method. In the first ANOVA, the independent variable will be subject group, and the dependent variable will be clinical tympanometric peak static acoustic admittance at 226 Hz. In the second ANOVA, the independent variable will be subject group, and the dependent variable will be wideband absorbance at ambient pressure averaged across half-octaves from 250 to 8000 Hz.

For the Secondary Outcome measure of Middle Ear Muscle Reflex Test, separate t-tests will be used to examine the difference in middle ear muscle reflex threshold between the clinical and wideband experimental methods within each subject group.

For the Secondary Outcome measure of Wideband Otoacoustic Emission Test, an ANOVA will be used to examine the differences across subject groups in transient evoked otoacoustic emission (TEOAE) signal-to-noise ratio (SNR) (averaged across half-octave bands from 1000 to 8000 Hz).

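### The primary outcome reduces each battery to one number, so it cannot support Aim 1's battery-against-battery conclusion

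*SAP*

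**What the plan says.** **Protocol, Study Protocol section, Aim 1.** The aim is accuracy in differential diagnosis, and the stated means is "comparing the sensitivity and specificity of the WB battery to the traditional immittance battery". Its target conditions are given as "disorders common in Veterans including tympanic membrane perforation and serous otitis media". The hypothesis that closes the section is also about whole batteries: wideband is expected to be the more accurate of the two.

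**Protocol, Methods, Testing.** Every subject receives both batteries in one visit. The clinical one is a "standard immittance test battery consisting of a tympanogram and acoustic reflex threshold testing". The wideband tests "include ambient absorbance, absorbance tympanometry and acoustic reflex threshold". Otoacoustic emissions are described there as a separate measurement.

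**SAP, Statistical Analysis Plan, primary outcome (Middle Ear Test).** The plan is that "separate ANOVAs will be used to examine differences across groups within each method". In the first ANOVA "the dependent variable will be clinical tympanometric peak static acoustic admittance at 226 Hz". In the second it is "wideband absorbance at ambient pressure averaged across half-octaves from 250 to 8000 Hz". Reflex threshold is a secondary outcome, tested by its own clinical-versus-wideband t-tests within each group.

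**The concern.** The claim to be tested concerns two batteries, but the primary analysis contains one reading from each. A reader of the final report will want to know whether the wideband battery identifies middle-ear disorder better than the battery audiologists now use. Two F-tests, one on peak admittance and one on averaged absorbance, cannot say so, however clear their results.

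Adding an accuracy measure would not cure this. An ROC curve for 226-Hz peak admittance set beside one for averaged absorbance would still compare two single measures. The risk is that a difference between them is reported as a difference between batteries, in either direction.

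**Working it through.** The plan states no sample size, significance level, effect size, standard deviation or target sensitivity, so it offers no figure to reproduce. The main check is to set the sections side by side.

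**1. What each battery contains and what the primary outcome uses**

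| | Protocol, Testing | SAP, primary outcome | Left out of the primary outcome |
|---|---|---|---|
| Clinical | tympanogram; reflex threshold | peak admittance at 226 Hz | any other tympanogram reading; reflex threshold |
| Wideband | ambient absorbance; absorbance tympanometry; reflex threshold | ambient absorbance, averaged over frequency | absorbance by band; absorbance tympanometry; reflex threshold |

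On the clinical side, one reading from one of two tests is used. On the wideband side, one average from one of three tests is used. Reflex threshold is analysed for both methods, but apart from the middle-ear measures and never combined with them.

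**2. What the primary analysis can conclude**

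Each ANOVA asks whether the group means of one measure differ. The primary-outcome paragraph has no cut-off, sensitivity, specificity, ROC curve or between-method contrast. The SAP's opening paragraph does plan within-group t-tests of method. Applied here, they would compare admittance with absorbance, which are different quantities, and would not measure diagnostic accuracy.

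**3. Whether the reduction favours one method (assumed inputs only)**

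Let d be the separation in standard deviations between middle-ear and other ears. In a binormal model AUC = Φ(d/√2), and sensitivity at 90% specificity = 1 − Φ(1.2816 − d).

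*Clinical side.* Let peak admittance have separation d₁. Add two further independent readings, each with separation d₂, so that d = √(d₁² + 2d₂²).

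- With d₁ = 1.0 and d₂ = 0.5, d = √1.5 = 1.225.
- AUC goes from Φ(0.707) = 0.760 to Φ(0.866) = 0.807.
- Sensitivity at 90% specificity goes from 0.39 to 0.48.
- Over d₁ = 0.5 to 1.5 and d₂ = 0 to 0.8, the AUC lost by using the single reading is 0.00 to 0.17. It is zero if the other readings carry no information.

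*Wideband side.* Half-octave centres from 250 to 8000 Hz number 2 × log₂(8000/250) + 1 = 11. Let m bands be informative, with d = 0.8 each, and let every pair of bands have correlation ρ. The plain mean has d = (0.8m/11)/√((1 + 10ρ)/11). The best linear combination has d = √(μᵀS⁻¹μ), where μ holds the band separations and S is the correlation matrix.

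- With m = 3 and ρ = 0.3, the mean has d = 0.218/0.603 = 0.362 and AUC 0.601. The best combination has d = 1.458 and AUC 0.849.
- Over m = 3 to 5 and ρ = 0 to 0.6, AUC is 0.58 to 0.80 for the mean and 0.84 to 0.94 for the best combination. The loss runs from 0.897 − 0.803 = 0.09 to 0.909 − 0.577 = 0.33.
- With all 11 bands equally informative, the mean loses nothing.

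The two ranges overlap and both include zero, so the direction of any net bias is undetermined. The wideband figures cover only the loss from averaging, not the loss from leaving out absorbance tympanometry. They are also a ceiling, since they assume that the best weights are known.

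**The case against.** **No comparison is planned, so there is nothing to bias.** The primary plan runs one ANOVA per method with no contrast between them. That is correct, and it rules out saying that wideband is tested against the clinical reading. It does not rescue the plan: these two ANOVAs are the only primary evidence offered for a comparative aim.

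**The comparator has been selectively weakened.** A reader might infer this from the single 226-Hz reading, especially beside a wideband measure that spans 250 to 8000 Hz. The documents do not support it. Wideband is reduced to one number by the same paragraph, and averaging over bands can cost as much as or more than dropping tympanogram readings. Neither document names the other readings taken from the tympanogram, and how much they add in this population is unknown. Enriching only the clinical side in a worked example would prejudge the answer.

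**Peak admittance fails to tell perforation from serous otitis media.** A reader might infer this too, since Aim 1 names both. The SAP puts all middle-ear disorders in one group, so it does not test that separation for either method.

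**Reflex is not dropped.** This is true: it has its own secondary outcome. It is still never joined to the middle-ear measures, so neither battery is evaluated as a whole.

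**Conclusion.** The point holds in symmetric form. Followed exactly, the primary analysis can show whether groups differ on 226-Hz peak admittance and whether they differ on averaged ambient absorbance. It cannot show that the wideband battery is better or worse than the traditional battery. That conclusion rests on the wording of the two documents and needs no numerical assumption.

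The size and direction of the loss do depend on assumptions. On the illustrative inputs, the reduction costs 0.00 to 0.17 in AUC on the clinical side and 0.00 to 0.33 on the wideband side. None of those inputs comes from the documents, so the figures support no claim of bias toward either method. The change should be made because Aim 1 otherwise has no primary analysis that matches it.

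**What to change.** In the SAP's primary outcome:

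1. Define one combination rule per battery from measures already collected. The clinical rule takes the recorded tympanogram readings, listed by name, plus reflex threshold. The wideband rule takes ambient absorbance, absorbance tympanometry and wideband reflex threshold.
2. Fix each rule before the data are examined, or derive it with cross-validation, so that neither method gains from being fitted and judged on the same ears.
3. Compare the two rules' sensitivity and specificity for the middle-ear group in the same subjects, by a paired method. Name the reference standard for middle-ear status and the groups in which specificity is estimated. If both ears of a subject are used, allow for their correlation.
4. Keep the two single-measure ANOVAs as descriptive. Limit any conclusion from them to 226-Hz peak admittance and averaged ambient absorbance.
5. Make no claim about telling one middle-ear disorder from another unless an analysis by disorder is added.

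The cost is SAP wording and slightly more analysis, with no new test or visit. Any wideband advantage may turn out smaller or larger than the single measures suggest. If the combined analysis is not adopted, item 4 alone would still keep the report from claiming more than its primary analysis can show.

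### Reflex thresholds are cut off at the stimulus limit, yet the methods are compared only by t-tests: the estimated difference is biased, towards zero if both methods share the limit and have similar error

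*SAP*

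**What the plan says.** Under Methods, Testing, the protocol describes the standard immittance battery as "consisting of a tympanogram and acoustic reflex threshold testing. Stimuli will not exceed a level of 100 decibels hearing level (dB HL". The next step reads "Finally, the wideband test battery will be performed with adults seated comfortably in a sound-treated booth", and that battery has its own reflex threshold: "The tests in the wideband battery are similar to the clinical admittance battery and include ambient absorbance, absorbance tympanometry and acoustic reflex threshold". No separate limit or unit is given for the wideband reflex test.

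The design is paired: "All subjects will receive the same clinical and WB test battery". Methods, Subjects defines the groups: "Data will be acquired from three groups of subjects with normal hearing, sensorineural hearing loss (SNHL), and middle ear disorders". Aim 2 in the Study Protocol section develops the wideband reflex test to "provide automatic detection of the ASR threshold for comparison with the traditional single-frequency ASR threshold".

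For analysis, the Statistical Analysis Plan gives a general rule, "T-tests will be used to examine effects of method (clinical vs. experimental wideband) within each subject group", and for the reflex outcome repeats that "separate t-tests will be used to examine the difference in middle ear muscle reflex threshold between the clinical and wideband experimental methods". The text available here does not say that the t-tests are paired or how an ear with no reflex is recorded and analysed.

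**The concern.** With a maximum stimulus level, a reflex that has not appeared by that level is not a missing measurement. It says that the threshold lies above the limit, so the value is right-censored. A t-test has no place for such a value. Whatever coding rule is adopted, the ear is either left out or entered as a number that nobody measured.

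Both choices act on the upper tail of the thresholds, and that tail need not be the same for the two methods. The mean difference that the t-test reports is then not the true method difference. The t-tests are run separately in three groups. If the groups differ in how often the reflex is absent, one and the same method difference will look different from group to group. That matters because this comparison is what the SAP offers for the Aim 2 question.

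**Working it through.** The documents give no sample size, SD, effect size or absent-reflex rate for this outcome, so there is no figure of the plan's own to reproduce. Only the 100 dB HL limit comes from the protocol. Every other input is an assumption made to show direction and scale.

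**Model.** Ear-level threshold T is normal with mean μ and SD 8. Clinical value C = T + e1 and wideband value W = T − d + e2, so d is the true excess of clinical over wideband. Error SDs are 4 and 4 unless stated. Both methods share the limit L = 100 unless stated.

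**Scored at the limit.** For X normal with mean m and SD s, and a = (L − m)/s:

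E[min(X, L)] = L − [(L − m)Φ(a) + sφ(a)].

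Here s = √(64 + 16) = 8.944. The estimated difference is the wideband bracket minus the clinical bracket. With d = 5:

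- μ = 85: (20 × 0.9873 + 8.944 × 0.0327) − (15 × 0.9532 + 8.944 × 0.0978) = 20.04 − 15.17 = 4.87 dB.
- μ = 95: (10 × 0.8682 + 8.944 × 0.2135) − (5 × 0.7119 + 8.944 × 0.3412) = 10.59 − 6.61 = 3.98 dB.
- μ = 105: (0 + 8.944 × 0.3989) − (−5 × 0.2881 + 8.944 × 0.3412) = 3.57 − 1.61 = 1.96 dB.

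The share of clinical reflexes absent is 1 − Φ(a), for example 1 − 0.7119 = 29% at μ = 95.

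**Pairs dropped** when either reflex is absent: simulated with 2,000,000 pairs per setting.

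| Clinical mean | Clinical reflex absent | Dropped | Scored at limit |
|---|---|---|---|
| 85 | 5% | 4.9 dB | 4.9 dB |
| 90 | 13% | 4.7 dB | 4.6 dB |
| 95 | 29% | 4.4 dB | 4.0 dB |
| 105 | 71% | 3.7 dB | 2.0 dB |

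**False positives.** With d = 0, 50 pairs, two-sided 0.05 and 10,000 trials, the paired t-test rejects in about 5% of trials under either rule.

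**Unequal error** (clinical SD 4, wideband SD 8, so wideband s = √(64 + 64) = 11.314), same shared limit:

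- True zero, μ = 95, scored: (5 × 0.6707 + 11.314 × 0.3618) − 6.61 = 7.45 − 6.61 = 0.84 dB. Dropped: 1.7 dB. False positives are 21% dropped and 13% scored.
- True 5 dB, dropped: 5.2, 5.5 and 5.5 dB at means 85, 95 and 105, an overstatement. Scored: 5.0, 4.6 and 2.9 dB.
- Errors reversed (8 and 4), true 2 dB, μ = 105: the estimate is negative under both rules, by more than 1 dB if pairs are dropped and by about 0.2 dB if scored.

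**Other inputs.** With total SD 10 in each method, correlation 0.7 and 30 pairs, a true 5 dB falls to between 4.8 and 2.0 dB (scored) or between 4.7 and 3.3 dB (dropped) as clinical absence rises from 7% to 69%. Power, about 93% without censoring, falls to 64% (scored) or 24% (dropped) at 69%. The bias can also almost vanish: with correlation 0.99, dropping pairs gives 4.95 of 5 dB at 31% absent.

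**The case against.** The strongest reply is that a t-test with a simple scoring rule may serve well enough. With a shared limit and equal error it keeps its 5% level and is good at detecting a difference. At 71% absent with a true 5 dB and 50 pairs, scoring at the limit gives 98% power, against 78% for a censored model with method-specific variances (68% for the t-test if pairs are dropped). At 5% absent the estimate is 4.9 of 5 dB, so there is almost nothing to repair. All of this stands. In that setting the defect is in the estimate, not in the test.

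It is also fair that the sizes rest on assumptions, that the outcome is secondary, and that a no-response rule could lie in SAP text not available here. The last point does not remove the problem, because any rule that feeds a t-test must still drop or score these ears.

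Two stronger readings are tempting. A reader might infer that the difference is always understated, so that the plan errs on the safe side. That needs similar error in both methods, and nothing in the documents supports this for a single-frequency test against an automated wideband one; with unequal error the bias can go either way. A reader might also infer that the two methods have different limits, which can inflate false positives sharply when scored at the limit. The documents do not say so. They leave the scope of the cap open.

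**Conclusion.** The point holds in conditional form. Right-censoring of the clinical threshold follows from the protocol's cap, and the SAP's named test cannot represent it. The estimated method difference is biased towards zero if limit and error are shared and no-response ears are dropped or scored at the limit. It may be overstated, spurious or reversed if they are not. The bias differs between groups if absent-reflex rates differ.

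Under the assumed SDs the loss on a true 5 dB runs from about 0.1 dB at 5% absent to between 1.3 dB (5 − 3.7, dropped) and 3.0 dB (5 − 2.0, scored) at 71% absent. The actual size cannot be known from the documents, and it is small where absent reflexes are rare. The documents do not support a claim that the plan's t-test inflates false positives in general: with a shared limit and equal error it does not. This should be fixed as a cheap improvement to a secondary analysis, with medium confidence. Clustering of two ears within a subject is a separate matter and arises only if both ears are analysed, which the text does not say.

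**What to change.** State in the SAP that the comparison is paired, what each method's stimulus limit and unit are, and how a no-response is recorded.

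- **Estimate.** Within each group, use a paired model that treats a no-response as right-censored at that method's own limit, with method-specific residual variances, provided both thresholds are on a common dB scale. Separate variances matter: with error SDs 4 and 8 and a true zero, a single residual SD gives a bias of 0.7 dB at mean 95.
- **Support.** Add a paired sign or rank test with no-response ranked highest, after cutting both methods at the lower limit. Keep the t-test, with its coding rule stated, as a sensitivity analysis.
- **Report.** Give the share with no reflex by method and group, with a McNemar comparison at a common limit.

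The cost is SAP wording and standard software. No stimulus level changes, and no new data are needed if no-responses and the highest level tested are recorded. The censored model leans on its distributional assumption as absent reflexes rise, and it can have less power than the scored t-test, as shown above. Its main gain is in the estimate: under the shared limit it returned 5.0 to 5.1 dB for a true 5 dB, with 5% to 7% false positives under a true zero (1,000 trials per setting). The sign test is not exact when errors are unequal and many reflexes are absent (11% false positives at mean 105 with SDs 4 and 8), so it should remain supporting.

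### The reflex-threshold analysis for Aim 2 tests only a mean offset; paired limits of agreement should be added to show how closely the two methods match in individual ears

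*SAP*

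**What the plan says.** The protocol's statement of Aim 2 is that a wideband acoustic reflex test will be modified to give "automatic detection of the ASR threshold for comparison with the traditional single-frequency ASR threshold".

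The SAP sets a general rule for comparing methods: "T-tests will be used to examine effects of method (clinical vs. experimental wideband) within each subject group". For the reflex outcome, which is secondary, it repeats that rule: "separate t-tests will be used to examine the difference in middle ear muscle reflex threshold between the clinical and wideband experimental methods", again within each of the three groups (normal hearing, sensorineural loss, middle ear disorder). It also says that "Bonferroni corrections will be applied for multiple comparisons", without giving the alpha or the number of comparisons.

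The Testing paragraph of the protocol shows that the data are naturally paired: "All subjects will receive the same clinical and WB test battery" and "Each subject will be tested in one laboratory visit". The same paragraph caps stimuli at 100 dB HL, in the sentence directly after the clinical immittance tests.

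The supplied text does not say whether the t-tests are paired or whether the unit is the ear or the subject. It names no limits of agreement, concordance measure or acceptable dB difference, and no rule for ears in which no reflex is found. Part of the SAP was not available for this review, so these absences are stated for the supplied text only. The paragraph on the reflex outcome does read as complete.

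**The concern.** When a new automatic threshold is set beside an established one, there are two separate questions. Is one method systematically higher than the other? How far apart are the two readings in a given ear? A t-test addresses only the first. Positive and negative differences cancel in the mean, so a detector that misses widely in both directions can show no significant difference. A detector that tracks the clinical threshold closely, apart from a small constant shift, can show a highly significant one.

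The second question matters because these thresholds are read one ear at a time. The protocol's overall hypothesis is also framed at that level, namely that "the WB test battery is more accurate than the traditional immittance test battery in identifying ears with normal auditory status". If the t-test is the only result reported for Aim 2, a reader learns about average offset and nothing about individual match. The result is then open to being read as agreement when it shows no such thing.

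**Working it through.** The documents give no sample size, alpha, standard deviation, expected offset or acceptable difference for this outcome, so there is no planned figure to reproduce. **Every number below is an assumption chosen to illustrate the principle.** None estimates what this trial will find.

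Set-up: d = wideband minus clinical threshold in the same ear, taken as Normal with mean b (offset) and standard deviation s, with n independent pairs and a two-sided 0.05 level.

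- Limits of agreement: b ± 1.96 × s.
- Share of ears with |d| > 10 dB: 1 − Φ((10 − b)/s) + Φ((−10 − b)/s).
- Chance that the paired t-test rejects: from the non-central t distribution with n − 1 degrees of freedom and non-centrality b√n/s.

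**Case 1: no offset, wide spread (b = 0).** The test rejects at its nominal 5% whatever s and n are, so it is non-significant 95% of the time. A simulation of 20,000 samples for each setting (s of 3, 5, 10 and 15 dB; n of 20, 50 and 100) gave rejection rates between 0.047 and 0.053.
- s = 8: limits ±1.96 × 8 = ±15.7 dB; share beyond 10 dB = 2 × (1 − Φ(1.25)) = 21%.
- s = 10: limits ±1.96 × 10 = ±19.6 dB; share beyond 10 dB = 2 × (1 − Φ(1.00)) = 32%.

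**Case 2: small offset, narrow spread (b = 2, s = 3, n = 30).**
- Limits: 2 ± 5.88, that is −3.9 to +7.9 dB.
- Share beyond 10 dB: 0.4%.
- Non-centrality: 2 × √30 / 3 = 3.65. The test rejects with probability 0.94.
- If the Bonferroni correction covers the three group tests (0.05/3 = 0.0167 each), the probability is 0.86.

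**Case 3: same offset and n, only the spread changed (b = 2, n = 50).**
- s = 3: rejection probability 0.996; 0.4% of ears beyond 10 dB.
- s = 10: rejection probability 0.28; 33% of ears beyond 10 dB.

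Case 3 is the cleanest comparison, because nothing differs but s. The test is more likely to flag the method whose individual readings match better. That is correct behaviour for a test of mean offset, and it is why the test cannot also serve as a measure of individual match.

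Precision of the proposed addition: the approximate 95% half-width for each limit is 1.96 × s × √(1/n + 1.96²/(2(n − 1))). With s = 10 dB this is 7.6 dB at n = 20, 4.8 dB at n = 50 and 3.4 dB at n = 100. The limits therefore need confidence intervals, especially within a group.

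**The case against.** The strongest reply is that agreement is not what the plan sets out to show. Aim 2 speaks of comparison, the SAP speaks of examining a difference, and the overall hypothesis is that the wideband battery is more accurate than the traditional one. On that view the clinical threshold is a comparator and not a reference standard, and wide limits could reflect error in the clinical method as much as in the new one. This stands. A reader might infer that the plan fails a stated agreement objective, but the documents contain none. A within-group t-test is a legitimate answer to the question of systematic offset.

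A reader might also infer that the trial will declare the methods equivalent after a non-significant test. The SAP contains no such decision rule. The risk is one of interpretation, which the plan does not guard against.

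Nor is it right to say that the spread of differences would never be obtained. A paired t-test computes it, and limits of agreement follow from the mean, standard deviation and n. What is missing is a plan to report and judge that spread, and a statement that the test is paired.

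On size, Cases 1 and 2 use different standard deviations, each suited to its point. With the 2 dB offset and n = 30, a standard deviation of 8 to 10 dB gives rejection only 26% to 19% of the time. The figures illustrate a principle and do not size a problem in this trial.

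Finally, limits of agreement have gaps of their own. Ears with no reflex at the stimulus limit have no numeric threshold and would drop out, as they would from the t-test. Two ears from one subject are not independent. The documents do not confirm that both thresholds are on the same dB scale. These points change the remedy but do not remove the need for it.

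What survives is narrower but sound: even a plain comparison of a new automatic threshold with an established one is incomplete if it reports only the mean offset.

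**Conclusion.** The point holds as a low-cost improvement to the analysis of a secondary outcome. The planned t-tests can show a systematic offset between methods. They do not report or judge how closely the automatic threshold matches the clinical one in individual ears, and a non-significant result must not be read as agreement.

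No size specific to this trial can be given. The logical part needs no assumed spread: with zero offset, a valid paired test stays non-significant at its nominal rate however wide the individual differences are. The dB figures rest on assumed values for offset, standard deviation, n, alpha and the 10 dB cut-off, and on normal, independent differences. No primary result is affected.

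**What to change.** Revise the SAP paragraph on the reflex outcome as follows.

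1. Keep the t-test for mean offset and state that it is paired. State which tests the Bonferroni correction covers.
2. For each group, add the mean paired difference with 95% CI, the 95% limits of agreement with CIs, and a check for trend of the difference with threshold level, shown on a difference-against-mean plot.
3. Read the limits against a dB margin that the investigators set before the data are examined. State that non-significance will not be interpreted as agreement.
4. State the unit of analysis. If both ears of a subject are used, allow for the clustering in both the test and the limits.
5. Express both thresholds on a common dB scale, or say how they are converted.
6. Cross-tabulate reflex present/absent by method within each group, so that ears with no reflex at the stimulus limit are counted and not silently dropped. State whether the 100 dB HL cap applies to both methods.

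The cost is SAP wording, slightly more analysis, and one more table and plot. Both batteries are already given to every subject in one visit, so no new measurements are needed.
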